Additionally, I will not initiate this study without written and dated approval from the appropriate Institutional Review Board (IRB)/Ethic Review Committee (ERC), and I understand that any changes in the protocol must be approved in writing by the Sponsor, the IRB/ERC, and, in certain cases the US Food and Drug Administration (FDA) or other applicable regulatory agencies, before they can be implemented, except where necessary to eliminate hazards to participants.

Principal Investigator's Signature

Date

Principal Investigator' Name (Print)

Lexicon Executive Vice President and Chief Medical Officer
(Signature)

Date

Lexicon Executive Vice President and Chief Medical Officer

1. Synopsis

Name of Study Drug	Telotristat ethyl (XERMELO®)
Protocol Number	LX1606.1-401-CS LX1606.401 (Abbreviated number)
Protocol Title	An Observational Study to Evaluate the Real-world Experience of Patients who are Initiating Treatment with Telotristat Ethyl (XERMELO)
Primary Objective	The primary objective of the study is to estimate the proportion of carcinoid syndrome (CS) patients who are satisfied with their overall symptom control, 6 months after initiating treatment with telotristat ethyl (XERMELO).
Secondary Objective	
The following secondary objectives will be assessed 6 months after initiating treatment with telotristat ethyl (XERMELO):
 
 • To estimate the proportion of patients reporting satisfaction of CS- related diarrhea control • To estimate proportion of patients reporting satisfaction of CS- related flushing control • To estimate the proportion of patients reporting reduction in rescue somatostatin analog (SSA) use • To estimate the proportion of patients reporting reduction in the dose of long-acting SSA injection • To estimate the proportion of patients reporting reduction in the frequency of long-acting SSA injection • To estimate the proportion of patients reporting an overall improvement in CS control after initiating XERMELO based on patient global impression of change (PGIC) • To estimate the proportion of patients that had a reduction in work-related absenteeism, presenteeism, activity impairment, and overall productivity loss after initiating XERMELO based on Worker Productivity and Activity Impairment: Specific Health Problem v2.0 (WPAI- SHP) • To estimate the proportion of patients reporting weight gain
Exploratory Objectives	[REDACTED]
Phase of Development	4

Methodology	
This observational, noninterventional, single-arm study will include patients with CS and who are initiating treatment with XERMELO. Patients will be asked to complete up to 7 web-based surveys including a Baseline assessment and then every 6 months for a total of up to 3 years. Each survey is anticipated to take no more than 20 minutes on average. All assessments, except mortality, will be patient-reported; medical records will not routinely be requested or reviewed as part of this observational study unless required for safety reporting purposes.
 
XERMELO prescription fill data will be collected directly from the specialty pharmacies, for all study patients that enter this study.
 
Upon entering the study, patients will be asked to provide sociodemographic information, current medical history (specifically date of CS and neuroendocrine [NET] diagnosis, NET location, CS-related hospitalization and/or ER visits, and NET-related surgery), height, weight, concomitant medications (specifically those related to SSA therapy, systemic therapy, and liver-directed therapy). In addition, patients will be asked to complete a work productivity and activity impairment (WPAI) assessment and describe satisfaction with CS, CS-related diarrhea and/or flushing prior to initiating treatment with XERMELO.
 
Patients will complete a survey every 6 months, describing changes to previously reported data and/or new occurrence of pre-specified events.
 
Data that may be collected at the 6 month time point includes changes in weight, concomitant medications (specifically those related to SSA therapy, systemic therapy, and liver-directed therapy), WPAI assessment, and satisfaction with CS, CS-related diarrhea and/or flushing following the initiation of treatment with XERMELO, as well as, new occurrence(s) of CS-related hospitalization and/or ER visit(s) will also be collected.
 
Following the month 6 time point, long-term assessments are to include changes in weight, concomitant medications (specifically those related to SSA therapy, systemic therapy, and liver-directed therapy), as well as, new occurrence(s) of CS-related hospitalization and/or ER visit(s) will also be collected.
 
Throughout the study information related to mortality will be collected through indirect sources.

Number of Patients	A minimum of 643 patients with CS who initiate treatment with XERMELO are expected to participate in this study.
Patients	Eligible patients are defined as adult patients (≥ 18 years) diagnosed with CS and initiating XERMELO as a new treatment.

Number of Study Sites	2
Treatments	250-mg XERMELO tablet administered as directed
Route of Administration	Oral
Duration of Participation	Up to 3 years
Inclusion Criteria	
Patients must meet all of the following criteria to be considered eligible to participate in the study:
 
 1. Adult, ≥ 18 years of age at the time of informed consent 2. A new, valid prescription for XERMELO 3. Initiating XERMELO for the treatment of carcinoid syndrome 4. Able and willing to provide informed consent prior to participation in the study
Exclusion Criteria	
Patients who meet any of the following criteria will be excluded from participating in the study:
 
 1. Unable to understand and read English 2. Unable to access the internet 3. Prior exposure to XERMELO
Statistical Methods	
The analysis population is comprised of all patients who provide consent, are enrolled into the study, and have data available for 1 or more of the primary and secondary endpoints. Descriptive statistics will be used to summarize the data. Continuous and ordinal variables will be summarized by n, mean, standard deviation, median, minimum, and maximum values. Categorical variables will be summarized by patient counts and related percentages.
 
Confidence limits (CLs) corresponding to point estimates of the proportions or means corresponding to the study endpoints will be 2-sided and calculated with 95% confidence coefficient. Statistical tests will be 2-sided and have an associated α-level=0.05.
 
For the primary endpoint, the proportion of CS patients who are at least somewhat satisfied with their overall symptom control at 6 months, a point estimate and the corresponding 95% CLs will be calculated based on the assumption of approximate normal distribution. Secondarily, a point estimate and corresponding 95% CLs will be calculated for the proportion of CS patients who are very satisfied with their overall symptom control at 6 months.
 
All the secondary endpoints correspond to proportions and will be summarized through point estimates and 95% CLs, as described above for the primary endpoint. In addition, for the primary and secondary endpoints, the frequency distributions of the categorical

	
responses and summary statistics of the corresponding ordinal values of the categories will be presented.
 
The incidences of at least 1 CS-related hospitalization, at least 1 CS-related ER visit, and mortality Baseline will be calculated at each 6-month interval. Kaplan-Meier estimates of each time-to-event variable, including quartiles, medians, and their corresponding 95% CLs, will be presented. The association or relationship between the primary endpoint and each long-term health outcome will be evaluated through descriptive statistics and the use of statistical models, as appropriate.

Assessments	Assessments include the following measures: patient satisfaction with CS, CS-related diarrhea and/or flushing control; PGIC; rescue SSA use; long-acting SSA dose and frequency; weight; productivity (WPAI-SHP); incidence of CS-related hospitalization(s), incidence of CS-related ER visit(s), and incidence of mortality.

Table of Contents

1. Synopsis	3
2. List of Abbreviations and Definitions of Terms	9
3. Introduction.....	10
3.1 Background on Telotristat Ethyl (XERMELO®) and Carcinoid Syndrome (CS)....	10
3.2 Rationale for Current Study	13
4. Study Objectives	13
4.1 Primary Objective	13
4.2 Secondary Objective	13
4.3 Exploratory Objective(s)	14
5. Investigational Plan.....	14
5.1 Overall Study Design	14
5.1.1 Survey Conduct.....	16
6. Study Population	17
6.1 Inclusion Criteria.....	18
6.2 Exclusion Criteria.....	18
6.3 Criteria for Stopping/Study Withdrawal	18
6.4 Criteria for Termination of the Study.....	18
7. Treatment	19
7.1 Telotristat Ethyl (XERMELO).....	19
7.2 Prior and Concomitant Medications.....	19
7.2.1 Prior Medications.....	19
7.2.2 Concomitant Medications	19
7.3 Prohibited Medications or Concomitant Therapy	19
8. Study Procedures	20
8.1 Restrictions during Study	20
8.2 Description of Study Assessments	20
8.2.1 Assessments	20
8.2.2 Other Assessments	21
8.3 Prescription Fill Data	22
8.4 Appropriateness of Assessments.....	22
9. Safety Reporting	22

9.1	Adverse Events.....	22
9.2	Definition of an Adverse Event.....	23
9.3	Assessment of Adverse Events	23
9.4	Follow-up of Adverse Events.....	24
9.5	Special Situations	24
9.5.1	Pregnancy.....	24
10.	Statistical Methodology	24
10.1	Determination of Sample Size.....	24
10.2	Analysis Populations	25
10.3	Study Endpoints.....	25
10.3.1	Primary and Secondary Endpoints.....	25
10.3.2	Other Endpoints	26
10.4	Statistical Methods	26
10.4.1	Analyses of Study Endpoints	27

3.1 Background on Telotristat Ethyl (XERMELO®) and Carcinoid Syndrome (CS)

Well differentiated neuroendocrine tumor (NET), formerly known as carcinoid tumor, is a relatively rare tumor type that arises from cells of the neuroendocrine system (Kulke, 2011; Turaga, 2011; Yao 2008).

Carcinoid syndrome (CS) occurs when well differentiated NETs secrete large amounts of serotonin and other vasoactive products into the systemic circulation. By one estimate, CS develops in approximately 10% of adult patients with well differentiated NET and, with a few exceptions, only manifests itself in the presence of liver metastasis (Tomassetti, 2001). By another estimate, approximately 8% to 35% of patients with NET have associated CS, with tumors of the small intestine carrying the highest risk (Rorstad, 2005). Classically, symptoms associated with CS include flushing, diarrhea, wheezing, abdominal pain, and valvular heart disease, although, a variety of other symptoms can occur. Roughly 75% of patients with CS experience diarrhea, which can occur either with or without other manifestations of the syndrome, and has perhaps the most direct impact on activities of daily living (Moertel, 1987).

Valvular heart disease has been associated with high serotonin levels (as measured by its metabolite, urinary 5-hydroxyindoleacetic acid [u5-HIAA]). Due to the slow growing nature of NETs and the prolonged course of disease, about 50% of patients with CS will eventually develop heart disease. Usually only metastatic NETs result in pathological changes to the heart as a result of the hypersecretion of vasoactive substances; in these cases, the development of cardiac pathology heralds a more precipitous decline in clinical course (Fox, 2004; Gustafsson, 2008; Turaga, 2011).

In epidemiological studies, high levels of u5-HIAA in patients with NETs have been associated with poor survival. van der Horst Schrivers, et al prospectively studied 76 patients with midgut well differentiated NETs (van der Horst Schrivers, 2007). Urine collected over a 24 hour period every 3 months was tested for u5 HIAA levels. Patients with high u5-HIAA levels (>20 mmol/mol creatinine) had a median survival of 33 months compared with 90 months for patients with a moderately high level (≤ 20 mmol/mol creatinine) (hazard ratio=3.33; 95% confidence limit [CL]: 1.66-6.66; $p=0.001$) (Turaga, 2011).

Morbidity Associated with Carcinoid Syndrome

For the patient with CS, severe diarrhea can lead to weight loss, electrolyte imbalance, malnutrition, and anxiety often resulting in social isolation. In a study of health-related

quality of life (QOL) using the European Organisation for Research and Treatment of Cancer (EORTC) Quality of Life Questionnaire (QLQ) C30 (version 3.0), patients with CS in Sweden reported a lower health-related QOL than the Swedish general population. A majority of patients reported higher levels of emotional distress, fatigue, and diarrhea, as well as worries about their prognosis, their families, and medical examinations (Fröjd, 2007). Issues with flushing, an intense reddening of the skin, produce considerable discomfort and impair social function. A higher bowel movement (BM) frequency is strongly associated with more reports of fatigue, sleep disturbance, anxiety, depression, pain, and worsening social and physical function. In a cross-sectional survey, undesirable associations were observed between a high number of BMs/day and domains including physical function, anxiety, depression, fatigue, pain impact, sleep disturbance, and social role, suggesting that a reduction in BMs could lead to a much better quality of life (Beaumont, 2012; Turaga, 2011).

The burden of symptoms associated with CS has been recently described in a global survey of 1,928 patients with NET (International Neuroendocrine Cancer Alliance [INCA], 2014; Turaga, 2011). According to the president of the INCA, the survey "...confirms for us the devastating impact this rare cancer can have on patients' lives". Diarrhea and flushing were prominent issues for patients in the survey. The majority of patients (92%) reported a lifestyle change as a result of their neuroendocrine cancer and 60% reported a negative effect on their emotional health. Patients commonly reported that their cancer led them to stop or to cut back on physical activity (49%) or on social life (43%).

Available Treatment Options

Somatostatin analogs (SSAs), like lanreotide and octreotide, are the cornerstone of therapy for the relief of CS and tumor stasis. Somatostatin analogs inhibit the release of serotonin by NETs and have become first line therapy for CS providing the most efficient treatment for the control of flushing, diarrhea, and other symptoms (Modlin, 2010).

Common side effects of SSAs are back pain, fatigue, headache, abdominal pain, nausea, and dizziness. Other side effects identified include biliary tract abnormalities (jaundice, gallstones, sludge, and dilatation), hyper- or hypoglycemia, hypothyroidism, and cardiac changes (sinus bradycardia, conduction abnormalities, and arrhythmias) (Novartis Pharmaceuticals Corp., Sandostatin® LAR Depot package insert, 2016).

Recently, results from the PROMID and CLARINET studies demonstrated the antiproliferative effects of octreotide and lanreotide autogel® (Caplin, 2014; Rinke, 2009).

Therefore, use of SSAs to reduce tumor proliferation has become increasingly common in the treatment paradigm for many patients with NET with or without symptoms.

In a substantial number of NET patients with CS, a tachyphylaxis to SSA treatment may occur as soon as 1 week and as long as 12.5 months after starting therapy (Garland, 2003; Moertel, 1987), possibly due to desensitization of the SSAs' effect on the somatostatin receptors (Hofland, 2003). This desensitization to SSAs may be overcome in some patients by increasing the dosage of SSA above the approved label; however, the efficacy and safety of higher doses is not yet established (Broder, 2015). Significant tumor progression might also contribute to the decrease in efficacy of SSAs over time.

Patients whose symptoms are generally controlled using long-acting SSA therapy may require supplemental doses of short acting SSA therapy when symptoms become exacerbated. Results of a 93 patient study with octreotide indicate approximately 35% to 40% of the patients who received the long-acting release (LAR) Depot formulation still require supplemental subcutaneous (rescue) therapy to control exacerbation of CS symptoms. After 6 months of treatment with octreotide, the number of patients requiring "rescue" doses increased to approximately 50% to 70% of patients. When a patient's response to SSA therapy declines, it is accepted practice to continue SSA therapy while initiating additional treatments, including additional prescribed and over the counter medications (Öberg, 2004).

Surgical debulking of tumors, radiation, various liver directed therapies, and chemotherapy may be attempted as a way of addressing overall tumor burden and reducing associated serotonin production (Kulke, 1999; Kulke, 2011; Öberg, 2012; Turaga, 2011).

Scientific Background for Development of XERMELO

Given the established role of serotonin in CS, inhibiting activity of tryptophan hydroxylase (TPH), the rate limiting enzyme responsible for the production of serotonin, should ameliorate symptoms and could perhaps avoid longer term disease sequelae.

XERMELO is a tryptophan hydroxylase inhibitor indicated for the treatment of carcinoid syndrome diarrhea in combination with SSA therapy in adults inadequately controlled by SSA therapy. Through inhibition of tryptophan hydroxylase, XERMELO reduces the production of peripheral serotonin, and the frequency of carcinoid syndrome diarrhea (Lexicon Pharmaceuticals, Inc., XERMELO™ package insert, 2017).

3.2 Rationale for Current Study

This observational study will capture patient experience with XERMELO in a real-world setting. XERMELO is the first orally available drug to be indicated for the treatment of CS diarrhea.

The clinical development program provided experience in more than 200 patients with CS and demonstrated statistically significant reductions in daily BM frequency, as well as an acceptable safety and tolerability profile. Data from 2 clinical studies, TELESTAR and TELECAST, support that the mechanism of action for XERMELO holds an important role in the treatment of CS. By reducing the production of peripheral serotonin, XERMELO is able to significantly reduce the frequency of CS diarrhea.

Patient satisfaction with XERMELO was not thoroughly studied in the clinical program and is not readily available in medical records. Results of a 35-patient interview sub-study conducted in TELESTAR after 12 weeks of blinded treatment indicated that nearly all patients reporting reductions in BM frequency during the Double-blind Treatment Period described them as meaningful, allowing them to better enjoy life and participate more in social and physical activities. Among interview participants (n=33) answering the question about satisfaction with the ability of the blinded study drug to treat CS, 50% of patients (12/24) on active treatment reported “very satisfied” while 0 patients in the placebo group reported the same term. The Sponsor assumes that satisfied patients will continue XERMELO to avoid the complications of CS, leading to better long-term outcomes ([Lexicon Pharmaceuticals, Inc., Clinical Study Report, 2017](#)).

Real-world experience with pharmaceutical products may only be evaluated once the product is available within the marketplace. In capturing patient experience, this study will also assess the patient journey though medical diagnosis of NET and treatment for CS in the clinical setting.

4. Study Objectives

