If the study team is unsuccessful in reaching the patient, the patient will be considered lost-to-follow up and the study team will update the enrollment status as appropriate.

Upon completion of the electronic consent and successful enrollment, the patient will be prompted to complete an online survey at Baseline, then every 6 months for a period of up to 3 years. All surveys will be completed online, at the patient's convenience, and in accordance with [Appendix A](#). The study team will provide technical support and reminder prompts, as described above, throughout the duration of participation.

At any time after Baseline, if the study team is unable to reach a patient after 3 attempts and the patient does not complete the survey within the prespecified window, the patient will be considered lost-to-follow up and the study team will disable the patient's unique study link as appropriate. Awareness by the specialty pharmacy of any change in the patient's status (ie, withdrawal of consent, treatment discontinuation) must be communicated to the study team. Should the specialty pharmacy communicate a patient's status change during the 3-year Follow-up Period, the study team will disable the patient's unique study link upon notification and no further survey invitations or reminders will be triggered.

Information regarding a patient's initial prescription and refill(s) will also be collected from the specialty pharmacies for all enrolled patients.

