5.1.1 Survey Conduct

An electronic consent and survey questionnaire approved by an Institutional Review Board (IRB) will be used by RTI to program the online survey for the purpose of standardizing responses among patients.

Each patient will complete up to 7 web-based surveys over the duration of the study. Each survey is anticipated to take no more than 20 minutes on average.

All assessments, except mortality, will be patient-reported; medical records will not routinely be requested or reviewed as part of this observational study unless required for safety reporting purposes. As patient recall over time may be limited, partial responses as in the case of dates of onset, and/or estimates of numerical information will be accepted.

Participation in the study is contingent on continued use of XERMELO. Each survey will establish ongoing treatment with XERMELO and continued consent to study participation prior to subsequent data collection.

The initial survey is intended to gather Baseline information, which may include:

- Sociodemographics (age, year of birth, sex, race, ethnicity, education, geographic region)
- Current medical history as it relates to CS, NET burden, NET location, and related conditions
 - Location of NET
 - Date of diagnosis; CS and NET
 - CS-related hospitalization(s)
 - CS-related ER visit(s)
 - NET-related surgery (eg, tumor debulking, lysis of adhesions)
- Satisfaction with CS, CS-related diarrhea and/or flushing control prior to starting XERMELO, where applicable
- Height and weight
- Concomitant medication as it relates to the following:
 - Long-acting SSA therapy

- Use of rescue medication - short-acting SSA
- Systemic tumor-directed therapy
- Liver-directed therapy (eg, chemoembolization)
- WPAI-SHP

The initial survey should be completed no later than 30 days, and subsequent surveys should be completed no later than 14 days, after the unique survey link has been provided to the patient via e-mail. Patients will be asked to complete a survey every 6 months for up to 3 years. The following patient-reported data may be collected as described in [Appendix A](#):

- Satisfaction with CS, CS-related diarrhea and/or flushing control after initiating XERMELO, where applicable
- PGIC
- Concomitant medication as it relates to the following:
 - Change in use of rescue medication - short-acting SSA
 - Change in long-acting SSA therapy
 - Systemic tumor-directed therapy
 - Liver-directed therapy (eg, chemoembolization)

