8.3 Prescription Fill Data

Information regarding a patient's initial prescription fill and subsequent refill(s) will be collected.

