3 DATA SOURCES AND VARIABLES

3.1 Data Sources

Data will be collected from patients electronically using web-based questionnaires. Patients who enroll in the study will complete a Baseline questionnaire within 30 days of enrollment and up to 6 Follow-up questionnaires at 6-month intervals after Baseline.

Prescription fill data, type of insurance, and reasons for discontinuation, including mortality, will be collected directly from the specialty pharmacy using a process that is still being determined and will be described in a separate document.

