3.2.5 Work Productivity and Activity Impairment Questionnaire—Specific Health Problem (WPAI-SHP)

The WPAI-SHP is a self-administered questionnaire ([Reilly et al., 1993](#)) comprising 6 questions that measure the effect of health problems on participants' ability to work and participate in regular activities based on their experiences in the previous 7 days. This questionnaire will be administered at Baseline and at the initial 6-month Follow-up.

The WPAI-SHP includes 4 domains (absenteeism, presenteeism, work productivity loss, and activity impairment). All participants will be asked whether they are employed (Q1) and how their CS-related problems affected their regular activities (Q6). Employed participants will be asked about hours of work missed due to CS-related problems (Q2), hours of work missed for any reason (eg, vacation, holidays, time off to participate in this study) (Q3), hours actually worked (Q4), and the degree that CS affected their productivity while working (Q5). An integer scale from 0 to 10 is used for Q5 and Q6, where 0 corresponds to no effect and 10 corresponds to complete effect.

Responses to the items are scored to produce the following 4 domains:

- Absenteeism: work time missed due to CS = [REDACTED]
- Presenteeism: impairment while working due to CS = [REDACTED]

- Work productivity loss: overall work impairment due to CS = [REDACTED]
[REDACTED]
- Activity impairment: activity impairment due to CS = [REDACTED]

Each score is then multiplied by 100 to express domains in terms of impairment percentages, with higher numbers indicating greater impairment and less productivity (ie, worse outcomes).

3.2.6 *Carcinoid Syndrome-related Health Care Resource Utilization*

At Baseline and at each Follow-up, questionnaire items will ask patients about ER visits and hospitalizations during the prior 6-month period. Data collected will include the following:

- The number of ER visits and the CS-related reason for each visit
- The number of hospitalizations, the number of nights for each stay, and the CS-related reason for each hospitalization

3.2.7 *Study Discontinuation and Mortality*

Patients will be terminated from the study if they discontinue the use of XERMELO, withdraw consent for participation, or are lost to follow-up. Information on reasons for discontinuation will be provided by the specialty pharmacy.

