5.1.5.4 Exploratory Analyses

Exploratory analysis of the association between patient satisfaction with overall CS symptom control at the initial 6-month Follow-up and the incidence of at least 1 ER visit, at least 1 hospitalization, and mortality will be performed as part of the final analysis. Only patients with non-missing data on satisfaction with overall CS symptom control at 6 months

will be included in the analysis. The satisfaction categories correspond to the binary categories used in the main analysis of the primary endpoint.

- Contingency table analysis to compare the incidence proportions of ER visits, hospitalizations, and mortality for each Follow-up interval and for the entire study period by satisfaction category, with chi-square tests for association. The satisfaction categories correspond to the binary categories used in the primary endpoint.
- Logistic regression models for the incidence of at least 1 ER visit and/or at least 1 hospitalization during the study period, with satisfaction category as a predictor variable. Covariates may be included in the models.

Additional or alternative exploratory analyses to be performed after data collection is complete will be determined in consultation with Lexicon and described in the final study report. The feasibility of each additional analysis will depend on the extent of data availability. Examples of additional analyses that may be considered are as follows:

- Kaplan-Meier analysis of mortality data, stratified by satisfaction category, including log-rank tests for differences between the strata.
- Kaplan-Meier analysis of time to first hospitalization, first ER visit, or mortality.
- Cox models for times to first ER visit, first hospitalization, and mortality, with satisfaction category as a predictor variable. Covariates may be included in the models.

Statistical tests will be 2-sided and have an associated alpha level of 0.05. The p-values from these tests will be considered descriptive rather than inferential.

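### ER visits and hospitalizations are seen only on XERMELO, so the planned satisfaction comparisons cannot show an effect acting through stopping, and over the whole study period may reverse it

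*Protocol*

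**What the plan says.** Protocol 3.2 sets out a three-step pathway: "The Sponsor assumes that satisfied patients will continue XERMELO to avoid the complications of CS, leading to better long-term outcomes".

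Follow-up is tied to the middle step. Protocol 5.1.1 states: "Participation in the study is contingent on continued use of XERMELO". Under Protocol 5.1, once the pharmacy reports a change of status, treatment discontinuation included, "the study team will disable the patient's unique study link upon notification and no further survey invitations or reminders will be triggered". SAP 3.2.7 agrees: "Patients will be terminated from the study if they discontinue the use of XERMELO, withdraw consent for participation, or are lost to follow-up". Protocol 6.3 does not list stopping XERMELO among its reasons for ending participation, so it does not match these sections.

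Protocol 5.1 also provides the data that describe continuation: "Information regarding a patient's initial prescription and refill(s) will also be collected from the specialty pharmacies for all enrolled patients". SAP 3.1 names these data as a source: "Prescription fill data, type of insurance, and reasons for discontinuation, including mortality, will be collected directly from the specialty pharmacy using a process". No SAP variable, endpoint or analysis then uses them. The only planned account of stopping is the disposition table in SAP 5.1.3.1, which gives the number, percentage and reasons for study discontinuation, not split by satisfaction.

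SAP 5.1.5.4 plans an "Exploratory analysis of the association between patient satisfaction with overall CS symptom control at the initial 6-month Follow-up and the incidence of" ER visits, hospitalizations and death. The firm methods are chi-square tests for each interval and for the whole study period, and logistic regression over the study period. Kaplan-Meier and Cox analyses appear only as possible extras, and none of them has discontinuation as its outcome.

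**The concern.** If satisfaction works by keeping patients on treatment, its effect shows up in the difference between patients who stay and patients who stop. Here the patients who stop disappear from the survey outcomes at the moment they stop. Two problems follow.

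First, within any one interval the comparison is between satisfied and dissatisfied patients who are all still on drug. An effect that acts through stopping has no way to appear.

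Second, over the whole period the group that stops sooner has fewer intervals in which an event can be reported. Neither a binary outcome of at least one event nor a logistic model without a term for observation time corrects for that. The dissatisfied group can look healthier simply because it was watched for less time.

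A reader of the report could take the first result to mean that satisfaction does not matter, and the second to mean that satisfied patients do worse. The link that the refill data could show, from satisfaction to continuation, would not be reported.

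**Working it through.** **The plan's own figures.** SAP 2.4 needs n = 1.96² × 0.5 × 0.5 / 0.05² = 384.15, rounded up to 385 month-6 responders, which matches. Enrolment after 40% dropout is 385 / 0.6 = 641.7, or 642 against the stated 643. The sample size is not at issue. The 385 are the patients expected to enter the satisfaction analysis.

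**Illustration.** The documents give no stopping or event rates, so these inputs are assumptions:
- five 6-month intervals, from month 6 to month 36;
- stopping probability d at the start of each interval: 0.10 if satisfied, 0.30 if dissatisfied;
- event risk per interval: 0.10 on drug, 0.20 off drug;
- satisfaction acts only through continuation.

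*Full follow-up.* Let on and off be the event-free proportions on and off drug. In each interval, off becomes (off + on × d) × 0.8 and on becomes on × (1 − d) × 0.9.
- Satisfied: after five intervals on = 0.81⁵ = 0.349 and off = 0.168, so risk = 1 − 0.517 = 48.3%.
- Dissatisfied: on = 0.63⁵ = 0.099 and off = 0.322, so risk = 1 − 0.422 = 57.8%.
- Odds ratio = (0.483/0.517) / (0.578/0.422) = 0.68, favouring satisfied patients.

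*As observed, per interval.* Everyone still under observation is on drug, so the risk is 10% in both groups and the comparison is null.

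*As observed, whole period,* counting a patient who leaves without an event as event-free:
- Satisfied: 0.9 × 0.1 × (1 − 0.81⁵) / (1 − 0.81) = 30.9%.
- Dissatisfied: 0.7 × 0.1 × (1 − 0.63⁵) / (1 − 0.63) = 17.0%.
- Odds ratio = (0.309/0.691) / (0.170/0.830) = 2.17, the wrong direction.

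**How far this depends on the inputs.**
- Stopping from 5% vs 15% up to 15% vs 40%, with event risks of 5%/10% or 10%/20% on/off drug: full follow-up odds ratio 0.68 to 0.80, observed 1.43 to 2.56.
- Stopping at the end of each interval instead of the start: 0.74 with full follow-up, 1.62 observed.
- Same event risk on and off drug (10%), stopping 10% vs 30%: 1.00 with full follow-up, still 2.17 observed. The distortion therefore comes from observation time, not from any drug effect.
- Adding the first six months, with 10% risk and everyone on drug: observed risks 0.1 + 0.9 × 0.309 = 37.8% and 0.1 + 0.9 × 0.170 = 25.3%, odds ratio 1.79. Full follow-up gives 53.5% and 62.0%, odds ratio 0.70.
- Equal stopping (10% in both groups): both odds ratios are 1.00.
- SAP 5.1.5.4 does not define the whole-period denominator. If only patients on drug throughout were counted, the risk would be 1 − 0.9⁵ = 41.0% in both groups: no reversal, but the pathway is again invisible.

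**Information available on time to discontinuation.** Schoenfeld's formula with two equal groups and two-sided 5% gives power = Φ(√(events × 0.25) × ln HR − 1.96).

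| Discontinuations after month 6 | HR | Power |
|---|---|---|
| 60 | 1.5 | 35% |
| 100 | 1.5 | 53% |
| 190 | 1.5 | 80% |
| 190 | 1.3 | 44% |

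The documents do not say how many discontinuations to expect. The 190 corresponds to about half of 385 responders stopping, which is an assumption.

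**The case against.** **The pathway is one background sentence.** Protocol 3.2 also describes the study as capturing real-world patient experience. The exploratory objective in SAP 2.2.3 is an association, not a mediation analysis, and p-values are descriptive. This stands: a reader might infer that the study fails its own purpose, and the documents do not support that. An association distorted by unequal observation time is still misleading when it is descriptive.

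**Continuation is not wholly ignored.** A reader might infer that it is never analysed. SAP 5.1.3.1 does tabulate study discontinuation with reasons, and stopping XERMELO is one cause of termination. What is missing is any analysis by satisfaction, as time to discontinuation, or from refill data.

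**Deaths are different.** A reader might infer that all outcomes end with treatment. Deaths come from pharmacy records (Protocol 9.1, SAP 3.2.7), and their capture after discontinuation is unspecified, not excluded. The interval denominator in SAP 5.1.5.1 does, however, require enrolment at the start of the interval.

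**Room is left open.** Protocol 4.3 is not readable in the public copy, so an objective on continuation there cannot be ruled out; SAP 2.2.3 lists none. The SAP defers the pharmacy data process and variable derivations to other documents and allows further exploratory analyses. None of this commits to the missing analysis.

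**Power may be low.** Protocol section 6 reports slow enrolment, with recruitment extended to six months before data collection ends, so late entrants add almost nothing after month 6. The documents also do not say whether fills are collected after a patient is lost to follow-up or withdraws. Both limits stand. Fills up to the stopping date would still date discontinuation.

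**Conclusion.** The point holds for CS-related ER visits and hospitalizations. Their planned association with month-6 satisfaction is on-treatment only. If dissatisfied patients stop sooner, as the sponsor's reasoning implies, the per-interval comparisons cannot show an effect acting through stopping, and the whole-period comparisons can be biased or reversed.

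The size is illustrative: an odds ratio of 2.17 observed against 0.68 with full follow-up. It rests on assumed stopping and event rates and on counting patients who leave as event-free. With equal stopping the distortion vanishes.

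A reader might infer that the planned tests must come out null, or that a positive result could not arise through continuation. Neither follows: continuation sets the length of observation, and that alone can produce an association over the whole period. Nor do the documents support a single power figure for the added analysis, since the number of discontinuations is unknown.

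The matter concerns an exploratory objective. It does not touch the primary endpoint or the sample size.

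**What to change.** In SAP 5.1.5.4:

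1. Add time from the month-6 survey to XERMELO discontinuation, from pharmacy refill and discontinuation records, by month-6 satisfaction category. Use Kaplan-Meier curves and a Cox model, both descriptive, and put a refill-gap definition in the variable specification.
2. Replace the whole-period logistic regression that lacks an observation-time term with a time-to-event or person-time analysis of ER visits and hospitalizations. Give whole-period chi-square results only alongside time under observation. The Cox model is already listed as a possible extra. In the illustration this removes the reversal, because the on-treatment rate is the same in both groups. It does not recover an effect that acts through stopping.
3. State in the report that these associations are on-treatment only and exclude any effect acting through stopping. State also whether deaths after discontinuation are captured and counted.

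Protocol 6.3 must also be reconciled with Protocol 5.1.1 and SAP 3.2.7 on whether stopping XERMELO ends participation.

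The cost is one added analysis, one changed model and a refill-gap definition, on data already planned and with no added patient burden. The month-6 starting point leaves out the expected 643 − 385 = 258 patients without a month-6 response, and precision depends on how many later discontinuations occur. The report should say both.
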